### **11.2 Analysis Populations**

The Full Analysis Set (FAS) includes all randomized participants who receive the allocated intervention and provide at least one primary outcome measurement. The Per-

Protocol Set (PPS) includes participants without major protocol deviations that could influence the primary outcome. The primary analysis will be performed on the FAS; sensitivity analyses may be repeated on the PPS if protocol deviations occur.

### **11.3 Handling of Missing Data**

The study is expected to have minimal missing data due to the short follow-up period. If missing data occur, the primary approach will be complete-case analysis. Reasons for missingness will be documented. No formal imputation strategy is planned.

### **11.4 Baseline Characteristics**

Baseline variables (age, sex, BMI, ASA class, and other demographic or clinical characteristics) will be summarized by group. Continuous baseline variables will be compared using one-way ANOVA for normally distributed data or Kruskal–Wallis test otherwise. Categorical variables will be compared using chi-square test or Fisher’s exact test when expected cell counts are less than five. Baseline comparisons will be interpreted descriptively.

### **11.5 Primary Outcome Analysis**

The primary outcome, total morphine consumption in the first 24 postoperative hours, will initially be assessed for normality. If the distribution is non-normal, the primary analysis will use the Kruskal–Wallis test to compare the three groups. If the overall test is significant ( $P < 0.05$ ), pairwise comparisons between groups (PENG vs AQLB, PENG vs Control, AQLB vs Control) will be conducted using Mann–Whitney U tests with

Bonferroni-adjusted significance thresholds. Median differences and 95% confidence intervals will be reported when appropriate.

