### **6.4 Postoperative Management**

In the post-anesthesia care unit (PACU), patients are monitored for 2 hours. NRS scores at rest and during movement, mean arterial pressure, and heart rate are recorded on arrival. On the ward, patients receive paracetamol 500 mg IV every 6 hours. Rescue analgesia consists of morphine 0.05 mg/kg IV bolus when NRS  $\geq 4$  at rest or during movement, with a maximum dose of 0.3 mg/kg in 24 hours. Ondansetron 0.1 mg/kg IV is administered for moderate or severe postoperative nausea/vomiting.

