## **7. Outcomes and Assessments**

### **7.1 Primary Outcome**

The primary outcome is total morphine consumption (mg) in the first 24 postoperative hours, calculated as the cumulative dose of intravenous morphine administered in the PACU and on the ward up to 24 hours after surgery.

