## **11.6 Secondary Outcome Analyses**

Total intraoperative fentanyl dose and other continuous secondary outcomes (such as time to first rescue morphine, time to ambulation, length of hospital stay, block performance time, and surgical duration) will be analyzed using one-way ANOVA for normally distributed data or Kruskal–Wallis test for skewed data, with appropriate pairwise post-hoc tests. NRS pain scores at rest and during movement and motor recovery scores will be analyzed at each time point using Kruskal–Wallis tests with Bonferroni-adjusted Mann–Whitney comparisons. Exploratory repeated-measures analyses (e.g., mixed-effects models) may be used to evaluate time-by-group interactions when assumptions are satisfied. Categorical outcomes, such as adverse event incidence and block failure rates, will be compared using chi-square or Fisher’s exact tests as appropriate.

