## **11.7 Subgroup and Sensitivity Analyses**

No formal subgroup analyses are pre-specified. Exploratory analyses may examine outcomes by sex, ASA class, or age category (e.g., 65–74 vs  $\geq 75$  years), clearly labeled as post-hoc. Sensitivity analyses may be performed excluding protocol deviations or extreme outliers in morphine consumption to evaluate the robustness of the primary findings.

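### Total morphine in mg carries body weight through its per-kilogram boluses, but 11.5 plans no weight-adjusted comparison: a cheap gain in precision, not a question of validity

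*Combined protocol and SAP*

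**What the plan says.** Section 7.1 defines the endpoint in absolute units: "The primary outcome is total morphine consumption (mg) in the first 24 postoperative hours". Section 6.4 doses by weight: "Rescue analgesia consists of morphine 0.05 mg/kg IV bolus when NRS" is at least 4, "with a maximum dose of 0.3 mg/kg in 24 hours". No other postoperative morphine regimen is described.

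For the comparison, 11.5 says: "If the distribution is non-normal, the primary analysis will use the Kruskal–Wallis test to compare the three groups". If that test is significant, the three pairs are compared by Mann–Whitney tests with Bonferroni correction. The section names no test for normally distributed data. For estimation it says: "Median differences and 95% confidence intervals will be reported when appropriate".

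Nothing elsewhere supplies a weight adjustment. Under 11.6, continuous secondary outcomes "will be analyzed using one-way ANOVA for normally distributed data or Kruskal–Wallis test for skewed data", again without covariates. Section 11.7 offers this: "Sensitivity analyses may be performed excluding protocol deviations or extreme outliers in morphine consumption". Section 11.4 reads: "Baseline variables (age, sex, BMI, ASA class, and other demographic or clinical characteristics) will be summarized by group". Weight is not named there, although the open-ended last item can include it.

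**The concern.** Two patients who need the same number of boluses receive different totals in mg if they differ in weight. At any one height, the BMI range in 4.1 (20 to 35) allows a 35/20 = 1.75-fold range of weight, and so of mg, for the same bolus count. A comparison in mg that ignores weight treats this spread as noise.

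Weight is fixed before randomization and must be known to give any dose. Adjusting for it is a standard way to remove such spread without recruiting more patients. What is at stake is a few points of power in a trial planned at 80%, not the credibility of a positive result.

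**Working it through.** **Inputs from the documents.** Three arms, α = 0.05, power 80%, effect size 0.35, N = 81 before attrition, hydromorphone 4.5 ± 2.9 mg (section 8); bolus 0.05 mg/kg, cap 0.3 mg/kg (6.4); BMI 20–35 (4.1).

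**Assumptions.** The documents give no weight SD, no bolus distribution and no relation between morphine need and weight. All counted morphine is taken to be given as the 6.4 bolus.

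**1. The plan's own figure.** Read 0.35 as Cohen's f in a one-way ANOVA. The noncentrality is N × f² = 81 × 0.1225 = 9.92, which gives 79.6% power. The smallest N reaching 80% is 82, so 81 is reproduced within rounding.

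**2. How weight enters.** Total mg = boluses × 0.05 × weight, with at most 0.3/0.05 = 6 full boluses. BMI spread evenly over 20–35 at one height gives a weight CV of (15/√12)/27.5 = 0.16; 0.12 to 0.20 is used as the range.

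**3. Analytic check, bolus count independent of weight.** The share of mg variance that a linear weight term removes is R² = CV²(weight)/CV²(mg). Section 8 suggests CV(mg) = 2.9/4.5 = 0.64, though for another opioid; its square is 0.415.
- Weight CV 0.12: R² = 0.0144/0.415 = 3.5%.
- Weight CV 0.20: R² = 0.04/0.415 = 9.6%.

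Replace f by f/√(1 − R²) and spend one degree of freedom. At N = 81, power rises from 79.6% to 80.7% at R² = 2.5%, 81.7% at 5% and 83.9% at 10%. The gain over the range above is therefore between about 1 and 4 points.

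**4. Simulation of the planned test.** 27 per arm (81/3), 20,000 trials per scenario. Weight is lognormal with mean 72 kg, clipped to 45–115 kg. Latent bolus need is normal, multiplied by 1 (independent of weight), √(72/weight) (half-dependent) or 72/weight (fixed in mg), then rounded and clipped to 0–6. The PENG-arm CV in mg is 0.62–0.71. Power in %, Kruskal–Wallis to Quade's rank ANCOVA, both on mg; weight CV 0.12, then 0.20:

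| Mean boluses PENG/AQLB/Control (SD) | Independent | Half-dependent | Fixed in mg |
|---|---|---|---|
| 2/2/3 (1.3) | 75.1 to 77.9; 71.9 to 76.5 | 76.9 to 77.7; 75.8 to 77.3 | 77.9 to 77.8; 77.7 to 77.8 |
| 2.5/2.5/3.7 (1.9) | 58.2 to 60.0; 55.6 to 59.2 | 60.3 to 61.0; 58.4 to 59.7 | 59.6 to 59.7; 59.0 to 59.0 |
| 2.5/2.5/4.1 (1.9) | 83.9 to 85.5; 81.3 to 84.8 | 85.0 to 85.6; 83.7 to 84.7 | 85.8 to 85.5; 85.0 to 85.0 |

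The gains are 1.6–4.6 points, about 0.5–1.5 points, and −0.3 to +0.1 points. The standard error of a gain is at most 0.22 points.

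In patients: in the 2/2/3 case at weight CV 0.20, unadjusted power rises from 71.9% at 27 per arm to 78.2% at 31. The 4.6-point gain is thus worth 4 × 4.6/6.3 = 2.9 patients per arm. At the low end (58.2% rising to 65.4%, gain 1.8) it is worth 4 × 1.8/7.2 = 1.0.

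**5. Normal data.** ANCOVA against ANOVA on the same data: +1.2 to +4.8, −0.1 to +1.1, and −0.7 to −0.4 points, in the same order.

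**6. Pairs.** One block arm against Control (overall test significant, then P < 0.05/3 = 0.0167): about +2 to +6, +1 to +2, and about zero. For PENG versus AQLB, an illustrative 2/2.5/3.2 boluses (SD 1.3) moves power only from about 12–13% to 13–15%.

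**7. Type I error.** 4.6–5.0% for Kruskal–Wallis and 4.9–5.3% for rank ANCOVA.

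**The case against.** The strongest reply is that an unadjusted rank test after randomization is a legitimate choice, and that the benefit rests on quantities the documents do not give. Both parts stand. Boluses are triggered by pain score, and nothing says whether a heavier patient's larger bolus delays the next request. The documents therefore cannot choose between a gain of a few points and none.

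A second objection is that a rank-ANCOVA P value has no matching adjusted estimate in mg, so the deciding test and the reported median difference could point different ways. This also stands. In the simulations the adjusted and unadjusted tests fell on opposite sides of 0.05 in about 2–10% of trials, with only the unadjusted test significant in 1.0–3.1%. That is a reason to state beforehand which test decides. A sponsor who puts agreement between test and estimate first could make the adjusted analysis supportive only, but would then give up the gain in the deciding test.

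Third, it may be too late. Ethics approval dates from March 2022 (section 5), and 11.8 speaks of interim analyses in the past tense. This does not show that outcome data have been seen, but the fix has to allow for it.

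The missing test for normal data in 11.5 is a separate gap and adds no weight to this point.

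**Conclusion.** The point holds as an optional, low-cost improvement in precision. Under the stated assumptions, the three-group test at 27 per arm gains about 1.5–4.5 points of power if bolus number is independent of weight, about 0.5–1.5 if half-dependent, and nothing if need is fixed in mg. Confidence in the size is moderate, because weight spread, bolus distribution and the need–weight relation are all assumed.

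A reader might infer more, but the documents do not support it:
- *That weight biases the primary comparison.* Allocation is randomized, weight is balanced on average, and type I error stays near 5%.
- *That the power loss is large.* Larger gains need less spread than section 8 suggests. With binomial counts (0–6) averaging 3.5/4.0/4.5 and a weight CV of 0.15, Kruskal–Wallis power was 67.2% on mg and 80.3% on mg/kg. The first arm's bolus CV there is √(6 × 0.583 × 0.417)/3.5 = 0.35, against 0.64 in section 8.
- *That mg is the wrong endpoint.* Nothing in the documents shows that need scales with weight, so there is no ground to replace mg by mg/kg.
- *That adjustment would rescue PENG versus AQLB.* No material gain is shown for that pair.

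**What to change.** Before unblinded data are seen, keep total mg as the primary outcome and add to 11.5:

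> The three-group comparison will be adjusted for baseline body weight. If the distribution is non-normal, Quade's rank ANCOVA will be used: rank mg and rank weight over all arms, regress the ranks of mg (response) on the ranks of weight (predictor), and compare the residuals between arms by one-way ANOVA. If normal, ANCOVA of mg on arm with weight as covariate will be used. After a significant overall test, each pairwise comparison repeats the same procedure within the two arms concerned (re-ranking within the pair) at 0.05/3 = 0.0167. The unadjusted Kruskal–Wallis and Mann–Whitney results and median differences in mg with 95% CIs will be reported alongside; the adjusted test decides if the two disagree.

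The direction of the regression must be explicit: regressing weight on mg instead gave only about 4–10% power in the same simulations. Name body weight among the 11.4 variables, and use mg/kg as a sensitivity analysis only.

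If data have already been seen, keep the unadjusted test as primary and report the adjusted analysis as supportive and added later.

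**Cost.** Wording in 11.4 and 11.5 and a little more analysis work; no extra patients, and no new measurement because weight is needed for dosing. The adjustment spends one degree of freedom and brings the estimate and disagreement issues described above. If need is fixed in mg and the data are normal, ANCOVA loses under 1 point of power.

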## **2. Study Objectives**

### **2.1 Primary Objective**

To compare total intravenous morphine consumption in the first 24 hours after surgery among three groups of elderly patients undergoing unilateral THA under general anesthesia: PENG block group, AQLB group, and Control group (opioid analgesia only).

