## **11. Statistical Analysis Plan**

### **11.1 General Principles**

Statistical analyses will be performed using IBM SPSS Statistics (version 28). All randomized participants who receive the allocated intervention and have outcome data will be included in the primary analysis (modified intention-to-treat). Two-sided tests will be used with a significance level of  $P < 0.05$ . Continuous variables will be assessed for normality using the Shapiro–Wilk test and visual inspection of histograms and Q–Q plots. Normally distributed variables will be presented as mean  $\pm$  standard deviation and non-normally distributed variables as median (interquartile range). Categorical variables will be presented as counts and percentages. Adjustment for multiple pairwise comparisons will use Bonferroni correction where applicable.

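### With three arms and a significant overall test required first, the Bonferroni split in section 11.5 is stricter than 5% familywise control needs and costs pairwise power; section 8's attrition arithmetic also falls short

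*Combined protocol and SAP*

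**What the plan says.** The primary objective (section 2.1) is a three-group one: "To compare total intravenous morphine consumption in the first 24 hours after surgery among three groups of elderly patients". Section 1 adds the pairwise questions: whether PENG or AQLB improves on opioid-based care, and how the two blocks compare.

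Section 11.5 sets the test sequence: "If the distribution is non-normal, the primary analysis will use the Kruskal–Wallis test to compare the three groups". Only if that test is significant at 0.05 are the pairs examined: "pairwise comparisons between groups (PENG vs AQLB, PENG vs Control, AQLB vs Control) will be conducted using Mann–Whitney U tests", with "Bonferroni-adjusted significance thresholds". Section 11.1 repeats the principle: "Adjustment for multiple pairwise comparisons will use Bonferroni correction where applicable". For reporting, section 11.5 adds: "Median differences and 95% confidence intervals will be reported when appropriate".

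Section 8 sizes the three-arm comparison. A standardized effect of 0.35, two-tailed alpha of 0.05 and 80% power give 81 patients, raised to 93 (31 per group) for roughly 15% attrition. It gives no power for any single pair.

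**The concern.** The plan protects against multiplicity twice. The overall test must be significant at 0.05 before any pair is examined, and each pair must then pass 0.0167. With three arms the first step already does most of the work, so the second gives up power that error control does not require. The loss falls on the pairwise comparisons, which are the ones that say which block works and whether the blocks differ.

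The attrition allowance has a separate slip. Multiplying 81 by 1.15 does not leave 81 after 15% are lost.

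**Working it through.** **Inputs.** Section 8: effect 0.35, alpha 0.05, 80% power, N = 81 (27 per arm), 93 enrolled (31 per arm). Section 11.5: overall test at 0.05, then three pairs at 0.05/3 = 0.0167. Assumption: 0.35 is Cohen's f, because section 8 does not name the index.

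**Step 1: reproduce section 8.** Noncentral F, three groups, noncentrality N × 0.35². At N = 81 this is 81 × 0.1225 = 9.92 and power is 79.6%, so 81 is reproduced as omnibus power. Power is 85.3% at N = 93. Reading 0.35 as a two-group d would need 129 per arm, so f is the reading that fits.

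**Step 2: why the split is not needed.** Call the pairwise nulls (equal distributions) PA, PC and AC.
- If any two are true, all three arms are equal. Every intersection of pairwise nulls is therefore the global null, which the overall test examines at 0.05.
- If exactly one is true, only one test can err, and it is run at 0.05.

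Rejecting a pair when both the overall test and that pair's test have P < 0.05 is therefore a closed procedure with strong familywise control. The argument is specific to three arms.

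**Step 3: familywise error by simulation** (normal data, 27 and 31 per arm, tie-corrected asymptotic rank tests).
- All arms equal: about 0.04 with the split, about 0.048 without.
- One pair equal, third arm different: about 0.016 with the split, 0.046–0.051 without.

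**Step 4: turn f into pairwise differences.**
- Equal blocks (means 0, 0, d): f = d√2/3, so d = 0.35 × 3/√2 = 0.742 versus Control.
- Evenly spaced arms (means 0, δ, 2δ): f = δ√(2/3), so δ = 0.35 × √1.5 = 0.43 for adjacent pairs and 0.86 for the extreme pair.

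**Step 5: power, Kruskal–Wallis then Mann–Whitney, normal data** (split → unsplit).

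| Claim | 27 per arm | 31 per arm |
|---|---|---|
| Equal blocks: each block vs Control | 57% → 69% | 64% → 76% |
| Equal blocks: at least one block vs Control | 73% → 77% | 80% → 83% |
| Equal blocks: both blocks vs Control | 41% → 60% | 49% → 68% |
| Evenly spaced: stronger block vs Control | 71% → 76% | 78% → 83% |
| Evenly spaced: each adjacent pair, including PENG vs AQLB | 18% → 32% | 21% → 36% |

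With equal blocks, the false PENG-versus-AQLB rate goes from about 1.6% to 5%.

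**Step 6: other shapes, equal blocks.** Section 6.4 gives boluses of 0.05 mg/kg ("Rescue analgesia consists of morphine 0.05 mg/kg IV bolus when NRS" reaches the threshold) "with a maximum dose of 0.3 mg/kg in 24 hours", so 0.3/0.05 = 6 boluses at most. Capped counts of this kind give each block about 49–64% with the split at 27 per arm and 56–71% at 31, depending on the assumed rates. The gain is 10–12 points. Strongly skewed gamma data built on section 8's 4.5 ± 2.9 run from 34% to 82% at 27, depending on how Control differs and which SD defines d.

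**Step 7: attrition.** 81 × 1.15 = 93.15, hence 93. But 93 × 0.85 = 79.05, so 15% loss leaves 79, with omnibus power 78.5%. The loss that leaves 81 is 12/93 = 12.9%. A full 15% allowance would be 81/0.85 = 95.3, or 96 at equal allocation.

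**The case against.** **Bonferroni is valid, and a conservative rule is a legitimate choice.** This stands. The split is not an error. The closed test has a real cost: more false PENG-versus-AQLB claims when the blocks are equal, on a comparison that section 1 names as an aim.

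**The gain depends on the pattern.** This also stands. The 11–12 points belong to each block separately when the blocks are equal. Section 1 can be read as asking whether either block is superior, and that claim gains only 3–4 points. Under even spacing the stronger block gains about 5.

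**Normal data would not reach these tests.** Section 11.5 sends only non-normal data to the rank tests and names no test for normal data. The normal figures are therefore a reference case. An ANOVA and t-test route gives each block 59% → 71% at 27 per arm and 67% → 78% at 31, so the conclusion does not hinge on this.

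**It may be too late.** Parts of the plan, such as section 11.8, are in the past tense. That does not show whether data have been unblinded, so the fix is conditional.

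**Stronger readings that the documents do not support.**
- A reader might infer that section 8 overstates its power. It does not: it describes a three-arm comparison, which matches section 2.1, and the figure reproduces. Not quoting pairwise power is missing detail.
- A reader might infer that a non-significant pair could not be interpreted. Section 11.5 plans median differences with confidence intervals, and these are what one would use.
- A reader might infer that the 95% intervals contradict the 0.0167 tests. Section 11.5 does not say whether they are adjusted, and section 11.1 applies Bonferroni where applicable, so no contradiction is established.

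**Conclusion.** The point holds as an available improvement, not as a flaw in validity. Behind a 0.05 overall test with three arms, the Bonferroni split buys protection beyond 5% familywise control. If 0.35 is Cohen's f and the data are normal, it costs 11–12 points of power for each block versus Control when the blocks are equal, about 14–15 points for adjacent pairs under even spacing, and only 3–5 points for the claim that at least one block works or for the stronger block. Power levels move considerably with the shape of the data and should not be read as forecasts. Closed testing does not bring each block to 80% at 31 per arm in the normal reference case (76%).

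The attrition figure in section 8 is wrong as written, but the effect is small: 79 rather than 81 evaluable patients, and 78.5% rather than 79.6% omnibus power.

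**What to change.** **Section 11.5, only if no unblinded data have been seen** (the documents do not show this). Replace the pairwise rule with: 'If the overall test is significant (P < 0.05), each pairwise Mann–Whitney comparison of the primary outcome is tested at two-sided 0.05 (closed testing, three arms); otherwise no pair is declared different.' In section 11.1, exempt these tests from the Bonferroni sentence. If unblinded data have been seen, keep Bonferroni as primary and show the unsplit results as a labelled sensitivity analysis.

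**Section 8.** Restate attrition as about 13%, or state that 15% loss leaves 79 evaluable patients and 78.5% omnibus power.

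**Optional clarifications.** Say in section 8 that the 80% is omnibus power, and in section 11.5 whether the 95% intervals are multiplicity-adjusted.

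**Cost.** A dated amendment of a few sentences and no more patients. The statistical price is the higher false PENG-versus-AQLB rate given above, and unsplit 95% intervals that are not simultaneous. Bonferroni-adjusted intervals can be shown alongside.

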## **11.6 Secondary Outcome Analyses**

Total intraoperative fentanyl dose and other continuous secondary outcomes (such as time to first rescue morphine, time to ambulation, length of hospital stay, block performance time, and surgical duration) will be analyzed using one-way ANOVA for normally distributed data or Kruskal–Wallis test for skewed data, with appropriate pairwise post-hoc tests. NRS pain scores at rest and during movement and motor recovery scores will be analyzed at each time point using Kruskal–Wallis tests with Bonferroni-adjusted Mann–Whitney comparisons. Exploratory repeated-measures analyses (e.g., mixed-effects models) may be used to evaluate time-by-group interactions when assumptions are satisfied. Categorical outcomes, such as adverse event incidence and block failure rates, will be compared using chi-square or Fisher’s exact tests as appropriate.

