## 6.2 Study Arms

### 6.2.1 PENG Block Group

After induction of general anesthesia and before surgical incision, patients in the PENG group are placed supine. A low-frequency curvilinear ultrasound probe (2–5 MHz) is positioned transversely over the anterior inferior iliac spine and rotated approximately 45° counter-clockwise along the pubic ramus. Key sonoanatomy includes the iliopubic eminence, iliopsoas muscle/tendon, and femoral nerve and vessels. A 22-G, 50 mm nerve block needle is inserted in-plane from lateral to medial to reach the fascial plane between the iliopsoas fascia and the pubic ramus, under the iliopsoas tendon. After negative aspiration and a 1 mL saline test injection, 30 mL of local anesthetic mixture (29 mL 0.25% bupivacaine plus 1 mL containing 4 mg dexamethasone) is injected with visualization of appropriate spread.

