### 6.2.2 Anterior Quadratus Lumborum Block (AQLB) Group

After induction of general anesthesia, patients assigned to the AQLB group are positioned in the lateral decubitus position with the operative side up. A low-frequency curvilinear ultrasound probe is placed horizontally above the iliac crest to visualize the transverse process, psoas major, erector spinae, and quadratus lumborum muscles. A 22-G, 50 mm needle is advanced in-plane from posterior to anterior into the fascial plane between quadratus lumborum and psoas major. Following hydro-localization with 1 mL

saline, 30 mL of 0.25% bupivacaine with 4 mg dexamethasone (29 mL + 1 mL) is injected in this plane.

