### **6.3 Intraoperative Analgesia and Monitoring**

Rescue analgesia consists of fentanyl 1 µg/kg IV if mean arterial pressure or heart rate increases more than 20% above baseline values. Hemodynamic variables (heart rate and mean arterial pressure) are recorded at baseline, 5 minutes after intubation, at skin incision, and then at regular intervals throughout surgery.

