### **7.2 Secondary Outcomes**

To compare intraoperative fentanyl consumption between the three groups.

To compare time to first rescue analgesia postoperatively.

To compare Numeric Pain Rating Scale (NRS) scores at rest and during passive 90° hip flexion at predefined postoperative time points (30 min, 2, 4, 6, 8, 12, 18, and 24 hours).

To assess block failure rate, defined as the requirement for more than one rescue morphine dose in the first postoperative hour.

To compare motor recovery (manual muscle test for quadriceps and iliopsoas, and active hip flexion range of motion) over the first 24 hours.

To compare time to first ambulation and length of hospital stay.

To compare intraoperative hemodynamic profiles (heart rate and mean arterial pressure).

To compare the incidence of block-related complications and morphine-related adverse events (e.g., nausea/vomiting, respiratory depression, hypotension, falls).

To compare block performance time and surgical duration between groups.

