## **9. Randomization, Allocation Concealment, and Blinding**

Randomization is based on a computer-generated sequence allocating patients to the three study groups in a 1:1:1 ratio. Allocation concealment is achieved using serially numbered, opaque, sealed envelopes prepared by a study coordinator not involved in patient care. Envelopes are opened only after induction of anesthesia. The anesthesiologist performing the block opens the envelope, prepares and administers the assigned intervention, and has no role in postoperative assessment. Patients, surgeons, ward staff, and outcome assessors are blinded to group assignment. Unblinding is permitted only if necessary for urgent clinical management, and the reason and timing are documented.

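### Section 11.6 names no analysis for heart rate and mean arterial pressure, and the default it leaves them with does not use the recorded baseline, at a cost in precision but not in validity

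*Combined protocol and SAP*

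**What the plan says.** Section 7.2 lists as a secondary outcome "To compare intraoperative hemodynamic profiles (heart rate and mean arterial pressure"). Section 6.3 gives the schedule: HR and MAP "are recorded at baseline, 5 minutes after intubation, at skin incision, and then at regular intervals throughout surgery". The length of the interval and the number of readings are not stated. The same section uses each patient's own baseline as the reference for intraoperative fentanyl, given "if mean arterial pressure or heart rate increases more than 20% above baseline values".

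Section 11.6 assigns one-way ANOVA or Kruskal–Wallis to "Total intraoperative fentanyl dose and other continuous secondary outcomes". The examples that follow do not include HR or MAP. Testing at each time point is specified only for NRS and motor scores. A further sentence permits exploratory repeated-measures analyses, mixed-effects models among them, for time-by-group interactions. It commits to nothing and mentions no baseline term.

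On timing, section 9 says "Envelopes are opened only after induction of anesthesia". Section 6.2.1 says "After induction of general anesthesia and before surgical incision, patients in the PENG group are placed supine", and section 6.2.2 says "After induction of general anesthesia, patients assigned to the AQLB group are positioned in the lateral decubitus position".

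**The concern.** The outcome is a series of readings per patient with a pre-treatment value of the same variable. The default test takes one value per patient and makes no use of that pre-treatment value. Stable differences between patients in blood pressure and heart rate then stay in the error term, although the data needed to remove part of them are already collected.

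The plan also does not define the outcome readings. It does not say whether the series is averaged, tested reading by reading or summarised in another way. Nor does it say whether the baseline and 5-minute post-intubation readings count as outcomes. The allocation is opened and the block prepared only after induction, so the baseline cannot carry a block effect and the 5-minute reading is due around or before the block. The analyst would make these choices after seeing the data, and a real difference between arms could be missed.

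**Working it through.** **The plan's own figure.** The documents give no power or sample size for HR or MAP. The only calculation, in section 8, is for opioid consumption. With three groups, an effect size of 0.35 read as Cohen's f, and two-sided α = 0.05, the noncentral F gives 79.6% power at N = 81 and first reaches 80% at N = 82. The stated 81 is thus reproduced to within one patient. Section 8 then sets the target at 93, or 31 per arm, which is used below.

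**Inputs**
- 31 per arm, N = 93, α = 0.05 two-sided (sections 8 and 11.1).
- Assumed: both blocks differ from Control by 0.5 SD, and PENG and AQLB do not differ.
- Assumed: correlation r between baseline and intraoperative value of 0.3, 0.5 or 0.6.

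**Unadjusted one-way ANOVA.** In SD units the arm means are 0.5, 0.5 and 0, with grand mean 1/3.
- f² = [(1/6)² + (1/6)² + (1/3)²] / 3 = 1/18.
- Noncentrality λ = 93 × 1/18 = 5.17, on 2 and 90 degrees of freedom.
- Power = 50%.

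**Baseline-adjusted (ANCOVA).** Error variance is multiplied by 1 − r², so λ becomes 5.17 / (1 − r²), on 2 and 89 degrees of freedom. Interval width is multiplied by √(1 − r²). The unadjusted sample of equal precision is 31 / (1 − r²) per arm.

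| r (assumed) | Error variance | Interval width | Equivalent n per arm | λ | Power |
|---|---|---|---|---|---|
| none (unadjusted) | 1.00 | 1.00 | 31 | 5.17 | 50% |
| 0.3 | 0.91 (−9%) | 0.95 | 34 | 5.68 | 54% |
| 0.5 | 0.75 (−25%) | 0.87 | 41 | 6.89 | 63% |
| 0.6 | 0.64 (−36%) | 0.80 | 48 | 8.07 | 71% |

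These figures are for one intraoperative value per patient. They show what baseline adjustment alone contributes and are not a power calculation for the mixed model proposed below.

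**Early readings, only if the series is pooled.** If K readings are averaged and one cannot carry a block effect, the average effect is multiplied by (K − 1)/K. The documents do not give K. For assumed K = 4, 6, 8 or 12 the factor is 0.75, 0.83, 0.88 or 0.92, a loss of 25% down to 8%. With the SD of the average held fixed, unadjusted power falls from 50% to 30% at K = 4 and to 43% at K = 12. If each time point is tested separately, the factor at the later times is 1 and nothing is lost there.

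**The case against.** A reader might draw four stronger conclusions. The documents support none of them.

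1. *The plan has chosen the wrong test for HR and MAP.* It has not explicitly chosen any. The one-way test is reached by inference from a list of examples that omits them, and the repeated-measures sentence is not limited to NRS. The defect is an omission, with an unadjusted default. The optional sentence does not fill the gap, because it is exploratory and states no baseline term.

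2. *The comparison is diluted.* That requires pooling, which no section specifies. Section 7.2 asks for profiles, and section 11.6 tests its other serial measures at each time point. Handled that way, an early reading adds a near-null comparison and leaves the later ones intact. In addition, only the baseline is certainly free of a block effect, since the plan gives no interval between intubation, block and incision. What stands is that the plan does not rule pooling out.

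3. *Rescue fentanyl and ephedrine mask differences, and adjustment would correct this.* Treatment given in response to readings may move them, but the documents give no basis for sizing that, and adjusting for baseline does not undo it.

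4. *The hemodynamic result would be invalid.* Under randomization the unadjusted comparison is unbiased.

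The strongest remaining objection is that the gain is modest if the correlation is low: about 4 points of power at r = 0.3. HR and MAP form one of nine listed secondary items, and no sample-size claim rests on them. This limits the importance of the point. It does not remove it, because the baseline is already recorded and using it costs almost nothing.

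**Conclusion.** The concern holds as a gap in specification and a loss of efficiency in a secondary outcome. The primary outcome is untouched. A baseline recorded for every patient is not used by the only non-exploratory rule that can reach HR and MAP. At 31 per arm, using it would cut error variance by 9%, 25% or 36% and raise power from 50% to about 54%, 63% or 71%. These figures rest on an assumed 0.5 SD difference of both blocks from Control and assumed correlations of 0.3, 0.5 and 0.6. The size of the gain is therefore uncertain. Its direction is not: any correlation large enough to repay one degree of freedom favours adjustment. Dilution by early readings is a conditional risk that arises only if readings are pooled. The change is worth making.

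**What to change.** Add to section 11.6 wording such as: *MAP and HR readings from skin incision onward will each be analysed with a linear mixed model with group, time, group-by-time interaction and the recorded baseline value as fixed effects and a random patient effect. Baseline and 5-minute post-intubation readings will be summarised descriptively by arm and are not outcomes.*

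Starting at skin incision presumes that the block is complete by then in both block arms. Section 6.2.1 places the PENG block before incision; section 6.2.2 says only after induction, so the SAP should state this presumption.

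Optionally, report ephedrine use by arm beside the fentanyl comparison already planned. This would help interpretation; it would not correct for rescue treatment.

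The cost is one paragraph of SAP text, one model per variable and one degree of freedom for the baseline covariate. No new data and no change to trial procedures are needed.
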